9.2.5 Handling of Multiplicity

The overall type I error rate of the primary and ranked key secondary endpoints for the two doses will be strongly controlled using a graphical multiple testing procedure [1]. Specifically, the testing will utilize the endpoint sequence of primary endpoint followed by the ranked key secondary endpoints in the order as specified in Section 9.2.3, and will begin with testing the primary endpoint using $\alpha/2$ for each dose ($\alpha = 0.0499$ accounting for 0.0001 spending after interim futility analysis). Continued testing will follow a pre-

specified α transfer path which includes downstream transfer along the endpoint sequence within each dose as well as cross-dose transfer.

The graph for the testing procedures is provided in Figure 2. In the graph, the arrows specify the α transfer paths. Once an endpoint is rejected (i.e., deemed significant) at its assigned significance level, its significance level will be transferred to subsequent endpoint(s) following the arrow(s). The numbers on the arrows denote the weights for transferring significance levels. Specifically, the weight 1 denotes 100% transfer of significance level.

Figure 2. Graphical Multiple Testing Procedure

[figure not shown]

Figure 2. Graphical Multiple Testing Procedure (Continued)

9.2.6 Efficacy Subgroup Analysis

The primary efficacy endpoint will be examined in the subgroups listed in Table 7 below. Treatment difference between each upadacitinib dose and the combined placebo group will be presented with point estimate and 95% confidence interval using normal approximation. No p-value will be provided for subgroup analysis.

[figure not shown]

Table 7. Subgroups for Efficacy Analysis

Subgroup Factor	Categories
Age	$<65, \ge 65 - <75, \ge 75$ years (if sample size allows)
Sex	Male or Female
BMI	$< 25 \text{ kg/m}^2 \text{ or} \ge 25 \text{ kg/m}^2$
Race	White, Non-white
Geographic region	North America, Western Europe and Oceania, Eastern Europe, Latin-America, Asia, and Other
Duration of PsA diagnosis	$\leq 5, > 5 - \leq 10, > 10 \text{ years}$
Baseline hsCRP	\leq ULN or $>$ ULN
Number of prior non-biologic DMARDs	≤1,>1
Current use of non-biologic DMARDs	Yes or No

[figure not shown]
9.3 Long-Term Efficacy Analysis

Assessments to evaluate long-term efficacy will be analyzed for the following measures at Week 2, 4, 8, 12, 16, 20, 24, 28, 32, 36, 44, 56 and every 12 weeks thereafter until completion of the study:

- ACR20/50/70 response rates
- Change from baseline in individual ACR components
- Change from baseline in DAS28 (CRP) and DAS28 (ESR)
- PsARC response rate
- Change from baseline in DAPSA
- Proportion of subjects achieving a clinically meaningful improvement in HAQ-DI (≥ 0.35)

Assessments to evaluate long-term efficacy will be analyzed for the following measures at Week 12, 24, 36, 56 and every 12 weeks thereafter until completion of the study:

[figure not shown]
- Change from baseline in EQ-5D-5L index and VAS score
- Change from baseline in FACIT-Fatigue
- Change from baseline in SF-36

- Change from baseline in WPAI
- Change from baseline in BASDAI
- Cumulative HRU
- Change from baseline in PASDAS
- BASDAI 50 response rates
- Change from baseline in ASDAS
- Proportion of subjects with ASDAS Inactive Disease
- Proportion of subjects with ASDAS Major Improvement
- Proportion of subjects with ASDAS Clinically Important Improvement

Assessments to evaluate long-term efficacy will be analyzed for the following measures at Week 12, 16, 24, 36, 56 and every 12 weeks thereafter until completion of the study:

- Change from baseline in BSA-Ps
- PASI 75/90/100 response rates
- Static Investigator Global Assessment (sIGA) of Psoriasis of 0 or 1 and at least a 2-point improvement from baseline
- Proportion of subjects achieving Minimal Disease Activity (MDA)
- Change from baseline in LDI
- Change from baseline in LEI
- Change from baseline in SPARCC enthesitis index
- Change from baseline in dactylitis count
- Proportion of subjects with resolution of dactylitis
- Proportion of subjects with resolution of enthesitis sites included in the LEI
- Proportion of subjects with resolution of enthesitis sites included in the SPARCC Enthesitis Index
- Change from baseline in total enthesitis count
- Proportion of subjects with resolution of enthesitis

Assessments to evaluate long-term efficacy will be analyzed for the following measures at Week 16, 24, 36, 56 and every 12 weeks thereafter until completion of the study:

[figure not shown]
• Change from baseline in SAPS

Additionally, assessments to evaluate long-term radiographic change will be analyzed for the following measures at Week 24, 56, 104, 152 and 260/PD visits:

- Change from baseline in SHS
- Change from baseline in joint space narrowing score and joint erosion score
- Proportion of subjects with no radiographic progression (defined as change from baseline in SHS ≤ 0);

Descriptive statistics based on AO will be provided for each randomized treatment group sequence as defined in Section 9.1.1. These include the number of observations, mean, standard deviation, 95% CI, median, minimum and maximum for continuous endpoints; and frequencies and percentages with 95% CI using normal approximation for binary endpoints. Plot for each randomized treatment group sequence over time will be provided for key endpoints. Additionally, treatment comparisons between each upadacitinib dose versus adalimumab will be made for efficacy endpoints for the originally randomized upadacitinib groups and adalimumab group. Point estimate, nominal p value and 95% CI will be provided up to Week 56. Treatment comparisons may also be provided after Week 56 as appropriate.

In addition, NRI approach and/or GLMM will be used for non-radiographic binary endpoint analysis, and MMRM will be used for continuous endpoint analysis. The analyses will be performed for the treatment sequences. The longitudinal analysis using MMRM or GLMM was described in Section 9.1.2. Point estimates and 95% CI from the model will be provided for each treatment sequence. Plot for each randomized treatment group sequence over time will be provided for key endpoints.

For radiographic related endpoints, the analysis will be based on linear extrapolation imputation and AO data. MMRM described in Section 9.1.2 will be conducted as mixed model based on AO data for Week 104 and future analyses.

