5.3.3.3 Additional Variables

The following outcome measures will be assessed in subjects treated with upadacitinib as compared to placebo and adalimumab when obtained at the scheduled time points in Appendix C other than those specified for the primary and key secondary variables:

- Proportion of subjects with no radiographic progression (defined as change from baseline in SHS ≤ 0);
- Change from baseline in joint space narrowing score and joint erosion score.
- Change from baseline in individual components of ACR response;
 - \circ Change from baseline in Tender Joint Count (TJC) (0-68);
 - Change from baseline in Swollen Joint Count (SJC) (0-66);
 - Change from baseline in Physician Global Assessment (PGA) Disease Activity (NRS);
 - Change from baseline in Patient's Global Assessment (PtGA) Disease Activity (NRS);
 - Change from baseline in Patient's Assessment of Pain Numerical Rating Scale (NRS);

- Change from baseline in Health Assessment Questionnaire Disability Index (HAQ-DI);
- Change from baseline in High-Sensitivity C Reactive Protein (hs-CRP);
- ACR 20/50/70 response rates;
- Change from baseline in Leeds Dactylitis Index (LDI);
- Change from baseline in dactylitis count;
- Proportion of subjects with resolution of dactylitis;
- Change from baseline in Leeds Enthesitis Index (LEI);
- Proportion of subjects with resolution of enthesitis sites included in the LEI;
- Change from baseline in SPARCC Enthesitis Index;
- Proportion of subjects with resolution of enthesitis sites included in the SPARCC Enthesitis Index;
- Change from baseline in total enthesitis count;
- Proportion of subjects with resolution of enthesitis;
- PASI 75/90/100 response rates (for subjects with ≥ 3% Body Surface Area (BSA) psoriasis at baseline);
- Proportion of subjects achieving a static Investigator Global Assessment of Psoriasis (sIGA) score of 0 or 1 and at least a 2-point improvement from baseline:
- BSA-Ps;
- Modified Psoriatic Arthritis Response Criteria (PsARC) response rate;
- Change from baseline in Disease Activity Score 28 (DAS28) (CRP);
- Change from baseline in DAS28 (ESR);
- Change from baseline in PsA Disease Activity Score (PASDAS);
- Change from baseline in Disease Activity in Psoriatic Arthritis (DAPSA) score;
- Change from baseline in Short Form 36 (SF-36) Health Questionnaire;
- Change from baseline in Functional Assessment of Chronic Illness Therapy (FACIT)- Fatigue Questionnaire;
- Change from baseline in EuroQol-5D-5L (EQ-5D-5L) Questionnaire;

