Activity	SCR D -35 to D -1	BL D	Wk 2 D 15	Wk 4 D 29	Wk 8 D 57	Wk 12 D 85	Wk 16 D 113	Wk 20 D 141	Wk 24 D 169	Wk 28 D 197	Wk 32 D 225	Wk 36 D 253	Wk 44 D 309	Wk 56 D 393	Wk 68 ^a to Wk 248 (Every 12 Wks) D 477 to D 1737	Wk 260 or PD D 1821	30 Day F/U Visit/ Call ^b D 1851	70- Day F/U Call ^b D 1877
Subject Questionnaires bb HAQ-DI Patient-Pain PtGA-Disease Activity	D-1	X	X	X	X	X	X	X	X	X	X	X	X	X	X X	X	1031	18//
Subject Questionnaires ^{bb} SF-36 EQ-5D-5L ⁱⁱ FACIT-F WPAI ⁱⁱ BASDAI		X				X			X			X		X	X	X		
Subject Questionnaire bb,cc SAPS		X					X		X			X		X	X ^{cc}	X ^{cc}		
Tender and Swollen Joint Counts	X	X	X	X	X	X	X	X	X	X	X	X	X	X	X	X		
Psoriatic Spondylitis Question		X																
PGA-Disease Activity		X	X	X	X	X	X	X	X	X	X	X	X	X	X	X		
HRU		X				X			X			X		X	X	X		
BSA Psoriasis ^{cc}		X				X	X		X			X		X	X ^{cc}	X ^{cc}		
PASI ^{cc}		X				X	X		X			X		X	X ^{cc}	X ^{cc}		
sIGA ^{cc}		X				X	X		X			X		X	X ^{cc}	X ^{cc}		
Leeds Dactylitis Index (LDI)		X				X	X		X			X		X	X	X		
Leeds/SPARCC Enthesitis Indicies (LEI)		X				X	X		X			X		X	X	X		

	SCR D -35 to	BL D	Wk 2 D	Wk 4	Wk 8 D	Wk 12 D	Wk 16	Wk 20	Wk 24	Wk 28	Wk 32	Wk 36	Wk 44 D	Wk 56	Wk 68 ^a to Wk 248 (Every 12 Wks) D 477 to	Wk 260 or PD	30 Day F/U Visit/ Call ^b	70- Day F/U Call ^b
Activity	D -35 to	1	15	29	57	85	113	141	169	197	225	253	309	393	D 477 to D 1737	1821	1851	1877
Adverse Event Assessment ^{dd}	X ^{dd}	X	X	X	X	X	X	X	X	X	X	X	X	X	X	X	X	X
Randomization		X																
Dispense Study Drug and Subject Diary ^{ee}		X		X	X	X	X	X	X	X	X	X	X	X	X^{jj}			
Calculation of TJC/SJC Responses ff,gg						X ^{ff}	X ^{ff}				X ^{gg}	X ^{gg}	X^{gg}	X ^{gg}	X ^{gg}			
Subject Diary Review			X	X	X	X	X	X	X	X	X	X	X	X	X^{jj}			

- a. These visits every 12 weeks are at: Wk 68, Wk 80, Wk 92, Wk 104, Wk 116, Wk 128, Wk 140, Wk 152, Wk 164, Wk 176, Wk 188, Wk 200, Wk 212, Wk 224, Wk 236, Wk 248.

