- w. A urine dipstick macroscopic urinalysis will be completed by the central laboratory at all required visits. A microscopic analysis will be performed in the event the dipstick results show leukocytes, nitrite, protein, ketones, or blood greater than negative or glucose greater than normal.
- x. FSH should be tested at Screening if the female subject is < 55 years of age AND has had no menses for ≥ 12 months AND has no history of permanent surgical sterilization (defined in Section 5.2.4).
- y. For China, Japan and South Korea, or where mandated by local requirements: for subjects with HBs Ab+ and/or HBc Ab+ and negative HBV DNA at Screening, the HBV-DNA PCR test should be performed again approximately every 12 weeks. Retesting approximately every 12 weeks is not necessary for subjects that have a history of HBV vaccine and HBs Ab+ and HBc Ab-. If necessary, HBV DNA PCR may be tested at unscheduled visits.
- z. At Week 2 and Week 4 visits, PK samples should be collected prior to oral study drug dosing and the subjects should take the study drug dose at the clinic after collecting the PK blood sample. However, if the subject normally takes the study drug dose at a time that is after the time of the scheduled study visit, the subject should follow the regular dosing schedule and the PK sample should be collected at any time during the visit.

M15-572 Protocol Amendment 8 EudraCT 2016-004130-24

- aa. PK samples should be collected at any time during the visit. Subject should follow the regular dosing schedule. Collect PK samples at Week 8, Week 12, Week 16, Week 20, Week 24, Week 32, Week 56, and at PD visit only for subjects who prematurely discontinue from study drug treatment prior to Week 56. No PK sample collection is required at Week 260.
- bb. Prior to other study visit procedures.
- cc. PASI, BSA-Ps, sIGA, and SAPS are to be done at Week 80, Week 104, Week 128, Week 152, Week 176, Week 200, Week 224, Week 248 (every 24 weeks after the Week 56 visit) and at the final study visit (Week 260).
- dd. Collect serious adverse events and protocol-related non-serious AEs that occur after a subject signs the informed consent; prior to the first dose of study drug.
- ee. At Week 24, all placebo subjects will be switched to blinded upadacitinib regardless of clinical response.

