5.2 Analysis Windows

Definition of Study Days (Days Relative to the First Dose of Study Drug)

Study Days are calculated for each collection date relative to the date of the first dose of study drug. It is defined as the number of days between the date of the first dose of study drug and the collection date. Study days are negative values when the collection date of interest is prior to the first study drug dose date. Study days are positive values when the collection date of interest is on or after the first study drug dose date. The day of the first dose of study drug is defined as Study Day 1, while the day prior to the first study drug dose is defined as Study Day –1 (there is no Study Day 0). Study days are used to map actual study visits to the protocol-specified study visits.

Definition of Analysis Windows

The following rules will be applied to assign actual subject visits to protocol-specified visits. For each protocol-specified study visit, a target study day will be identified to represent the corresponding visit along with a window around the target day. Windows will be selected in a non-overlapping fashion so that a collection date does not fall into multiple visit windows. If a subject has two or more actual visits in one visit window, the visit closest to the target day will be used for analysis. If two visits are equidistant from the target day, then the later visit will be used for analysis.

The visit window and the target study day for each protocol-specified visit in Period 1 are displayed in Table 1, Table 2, Table 3, Table 4, Table 5 and Table 6 (depending on the different visit schedules of different endpoints). Visit windows for protocol-specified visits in Period 2 are defined similarly.

Table 1. Analysis Windows for Efficacy Analysis for Period 1 (for ACR Components, TJC28, SJC28, ESR and Derived Endpoints^a) and Safety Analysis for Period 1 (for Lab Values [Clinical Chemistry, Hematology, Urinalysis] and Vital Signs/Weight)

Protocol Specified Visit Week	Lower Bound	Target Day	Upper Bound
Baseline		1 ^b	1
2	2	15	22
4	23	29	43
8	44	57	71
12	72	85	99
16	100	113	127
20	128	141	155
24	156	169	Min (183, first dose date from Week 24 dispensed kit)
28	Min (183, first dose date from Week 24 dispensed kit) + 1	197	211
32	212	225	239
36	240	253	281
44	282	309	351
56	352	393	435

a. ACR20/50/70 response rates, DAS28 (CRP), DAS28 (ESR), PsARC, DAPSA, proportion of subjects achieving a clinically meaningful improvement in HAQ-DI (≥ 0.35).

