9.1.2 Handling of Missing Data and Intercurrent Events

Non-Responder Imputation (NRI) Approach

The NRI approach will handle data for binary endpoints as follows.

- Subjects who prematurely discontinue from study drug will be considered as non-responders for all subsequent visits after discontinuation.
- In addition, any subject with any missing value for the binary endpoints at a specific visit will be treated as non-responder for that visit.

NRI data handling will be used for the primary estimand (refer to Section 9.2.1) for the binary endpoints.

Mixed-Effects Model Repeated Measures (MMRM) Up to Week 24

The repeated measure analysis will be conducted using mixed models including observed data at all visits. For the MMRM analysis, data collected after premature discontinuation

of study drug will be excluded. The mixed model includes the categorical fixed effects of treatment, visit, treatment-by-visit interaction, the stratification factor current DMARD use (yes/no) and the continuous fixed covariates of baseline measurement. An unstructured variance covariance matrix will be used. The parameter estimations are based on the assumption of data being missing at random (MAR) and using the method of restrictive maximum likelihood (REML). MMRM will be used for the primary estimand of the non-radiographic continuous endpoints (refer to Section 9.2.3).

[figure not shown]
Linear Extrapolation for Radiographic Data

For radiographic data (i.e., SHS-based endpoints), linear extrapolation will be applied to subjects with missing data including those due to premature discontinuation of study drug or meeting the rescue criteria, where the missing x-ray at the time point of interest will be imputed assuming a linear relationship across visits. Linear extrapolation will be used to facilitate the primary estimand for radiographic endpoints (refer to Section 9.2.3). Linear extrapolation will not be provided for Week 104 analysis and future analyses.

As Observed (AO)

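### SAP 9.3 schedules skin endpoints, SAPS and MDA every 12 weeks after Week 56, but 8 of those 17 visits have no scheduled skin data and the NRI rule makes no exception for them

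*SAP*

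**What the plan says.** SAP 9.3 groups BSA-Ps, PASI 75/90/100, sIGA 0/1 and MDA with the dactylitis and enthesitis measures and schedules all of them "at Week 12, 16, 24, 36, 56 and every 12 weeks thereafter until completion of the study". SAPS has a separate list with the same 12-week spacing after Week 56.

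Protocol Appendix C collects less. Footnote cc states that "PASI, BSA-Ps, sIGA, and SAPS are to be done at Week 80, Week 104, Week 128, Week 152", and it continues in 24-week steps to Week 248, plus Week 260. The dactylitis row and the enthesitis row (which begins "Leeds/SPARCC Enthesitis Indicies (LEI") carry no such footnote, so those measures are collected at every Period 2 visit. The same holds for joint counts, pain, patient global assessment and HAQ-DI.

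On methods, SAP 9.3 starts from As Observed descriptives and then says: "In addition, NRI approach and/or GLMM will be used for non-radiographic binary endpoint analysis". SAP Appendix F names both GLMM and NRI for long-term efficacy. The NRI rule in SAP 9.1.2 reads: "In addition, any subject with any missing value for the binary endpoints at a specific visit will be treated as non-responder for that visit".

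On windows, SAP 5.2 tabulates Period 1 only and adds: "Visit windows for protocol-specified visits in Period 2 are defined similarly". Protocol 5.3.3.3 covers the additional efficacy variables "when obtained at the scheduled time points in Appendix C". SAP 9.3 also promises: "Plot for each randomized treatment group sequence over time will be provided for key endpoints".

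**The concern.** The SAP asks for skin results at visits where the protocol does not plan to collect them, and its NRI rule does not separate a value that was missed from a value that was never due. If a programmer builds the tables from the 9.3 list and applies the rule as written, PASI and sIGA response would drop to about zero at alternate visits and recover at the next, in every treatment sequence. The PASI and sIGA artefact would be easy to spot. The one in MDA would not, because six of its seven criteria are still collected at those visits, so the rate would look plausible while being too low. SAP version 4.0 governs the remaining long-term reporting, so the text still matters.

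**Working it through.** **1. Visit counts.** Protocol Appendix C, footnote a, lists 16 visits from Week 68 to Week 248. Adding Week 260 gives 17, which is what every 12 weeks after Week 56 means in SAP 9.3. Footnote cc lists Weeks 80, 104, 128, 152, 176, 200, 224 and 248 (8 visits) plus Week 260, so 9. The difference is 17 − 9 = 8: Weeks 68, 92, 116, 140, 164, 188, 212 and 236.

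SAP 11.1 and 12.0 tie the added NRI/GLMM analysis to Week 104 and later. From Week 104 to Week 260 there are (260 − 104)/12 + 1 = 14 visits, of which 8 have skin data and 6 do not (116, 140, 164, 188, 212, 236).

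**2. Neighbouring skin data do not fill the gap.** Assume 12-week windows cut at midpoints, as in Period 1. Week 68 is Day 477, and its window runs from Day 436 to Day 519. A Week 80 visit (Day 561 ± 7) falls on Days 554 to 568. The SAP lets partial data be combined within a window, but an on-schedule Week 80 skin assessment is not in the Week 68 window.

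**3. PASI and sIGA.** With no assessment, the value is missing. Under the 9.1.2 rule the response rate at the eight visits is near 0%. As Observed would be nearly empty. It would not be wholly empty, because the Week 260 column also serves premature discontinuation, and any procedure may be done at an unscheduled visit. For BSA-Ps and SAPS, which are continuous, the consequence is nearly empty rows and visit terms that cannot be usefully estimated.

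**4. MDA.** SAP 9.4.12 calls a subject a responder if at least 5 of 7 criteria are met and a non-responder if at least 3 are not. Of the 128 patterns of seven yes/no criteria, 29 are MDA. With the skin criterion absent, 14 of these remain determinable (at least 5 of the other 6 met) and 15 do not (exactly 4 of 6 met, plus skin).

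Take subjects on study drug with the six non-skin criteria observed. Let a be the share meeting at least 5 of them, b the share meeting exactly 4, and p the share of that second group who meet the skin criterion.

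- Full seven-criterion rate: a + b·p
- NRI rate: a, so the error is −b·p, never positive
- As Observed rate: a/(1 − b), so the error is b·(a/(1 − b) − p), which can take either sign

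The documents give none of a, b or p. Two assumed cases show the signs only:

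| a | b | p | Full rate | NRI | As Observed |
|---|---|---|---|---|---|
| 0.26 | 0.155 | 0.8 | 38.4% | 26.0% | 30.8% |
| 0.40 | 0.15 | 0.3 | 44.5% | 40.0% | 47.1% |

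Simulations under two different sets of assumed criterion rates and correlations put the NRI shortfall at 1.7 to 20.7 points and at about 7 to 28 points. That spread reflects the chosen inputs, so no single figure should be quoted.

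**5. EQ-5D-5L and WPAI.** SAP 9.3 lists these every 12 weeks too. Footnote ii collects them six-monthly after Week 152. Reading six months as 24 weeks plus Week 260, four of the nine later visits have no scheduled data (164, 188, 212, 236). NRI does not apply to these scores, so this is a list correction only.

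**The case against.** The best defence is the window rule. SAP 5.2 makes windows depend on each endpoint's own visit schedule. Table 4, footnote a, places MDA with the skin, dactylitis and enthesitis measures, not with the ACR components. In Period 1 that leaves MDA without an analysis visit at Weeks 2, 4, 8, 20, 28, 32 and 44, although joint counts, pain, patient global assessment and HAQ-DI are collected then. Carried into Period 2, the same practice could put both the skin endpoints and MDA on the 24-week schedule. Protocol 5.3.3.3 points the same way. A reader might infer that windowing cannot rescue MDA because its other criteria are collected. Table 4 does not support that.

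This stands as a possible reading, but it does not settle the matter. It contradicts the explicit 9.3 list. Table 4 also holds LDI and LEI, which stay 12-weekly in Period 2, so one Period 2 table built on the same pattern would contain the eight visits. SAP 9.3 gives x-rays their own sparse list, so the section does follow the collection schedule where that was intended.

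NRI is also not the only route. SAP 9.3 offers it as an alternative or addition to GLMM, and As Observed comes first. That is correct, and it makes the 0% result conditional. GLMM is no remedy, however. It uses As Observed data with visit and treatment-by-visit terms, so it has almost nothing to fit for PASI and sIGA at those visits and loses the undetermined MDA subjects.

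Carrying the skin criterion forward would reduce the MDA error, but the SAP specifies component carry-forward only for ACR (9.4.1). The remaining objection, that a 0% row would be noticed, holds for PASI and sIGA but not for MDA.

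**Conclusion.** The schedule mismatch is certain: 8 of 17 listed visits after Week 56 have no scheduled skin data, or 6 of 14 if NRI begins at Week 104. The consequence is conditional. If the 9.3 list is followed and NRI is used, PASI and sIGA response is near 0% at those visits and MDA is too low by b·p. As Observed is nearly empty for the skin endpoints and drops the undetermined MDA subjects.

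Three stronger inferences are not supported. The documents do not show that these results will be reported, since endpoint-specific windows or a GLMM-only choice remain open. They give no size for the MDA error. They also do not put the main results at risk: SAP 11.1 states that the primary analysis and Period 1 reporting were completed under version 3.0. Treatment comparisons after Week 56 are optional, so what remains is long-term and essentially descriptive. Whether PASI, sIGA or MDA would be among the key endpoints plotted over time is not stated in 9.3. The text should be corrected before the remaining long-term reports.

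**What to change.** In SAP 9.3, limit PASI, sIGA, BSA-Ps, SAPS and MDA after Week 56 to Weeks 80, 104, 128, 152, 176, 200, 224, 248 and 260, and keep the dactylitis and enthesitis measures every 12 weeks. Visits without planned skin data then fall from 8 of 17 to 0 of 9. In SAP 9.1.2, state that NRI applies only at visits where the assessment is scheduled, meaning all components for MDA. As a list correction, align EQ-5D-5L and WPAI after Week 152 with protocol footnote ii.

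This changes SAP wording only and needs no new data. The cost is that MDA is no longer tabulated at eight visits where it could be determined for part of the subjects.
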